22.5.1 MULTIPLE IMPUTATION ANALYSIS

The mixed model for repeated measures (MMRM) allows for inclusion of patients with missing Week 10 values. If all subjects have at least one follow-up evaluation, the following MMRM will be utilized for the primary superiority test. If there are subjects without at least one post baseline assessment, the multiple imputation analysis summarized below will be the primary analysis method. Least squares estimated values from the MMRM will be reported for HDRS-17 at each visit and as such these estimates include implicit imputations of missing values.

Details of the MMRM used to evaluate the primary endpoint are described in the attached Statistical analysis plan.

22.6 MISSING DATA/SENSITIVITY ANALYSIS

Details of the handling are in the attached Statistical analysis plan.

22.7 COVARIATES/COVARIATE ANALYSIS

The heterogeneity of treatment effects for the primary effectiveness endpoint will be examined for subgroups using baseline variables. These will include, but are not limited to, age (split at median), and sex at birth. Subjects on antidepressants and/or psychotherapy drugs during the course of the trial will constitute their own subgroup and be characterized and described in the clinical study report. The mixed model for repeated measures will be run to see the impact of the treatment effect by each subgroup of interest separately. The results will be reported as mean differences and 95% confidence intervals for each subgroup. These results will be graphically displayed in a forest plot.

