14 DESCRIPTION OF STUDY PROCEDURES

DEMOGRAPHICS

At screening, participant baseline characteristics including, but not limited to, age and gender, will be recorded.

PAST MEDICAL HISTORY

At screening, each participant's past medical conditions and surgical procedures will be recorded.

PREGNANCY DETERMINATION

Prior to treatment, female participants of childbearing potential will be asked during the Screening visit whether they are pregnant or breastfeeding or plan to become pregnant or breastfeed during the trial.

CLINICIAN AND PATIENT REPORTED OUTCOME QUESTIONNAIRES (CLINROS/PROS)

The following Clinician or Patient Reported Outcome questionnaires will be completed and used to compare participant outcomes at follow-up time points compared to baseline:

Montgomery–Åsberg Depression Rating Scale (MADRS) - ClinRO

CONFIDENTIAL Page **43** of **69**

The Montgomery–Åsberg Depression Rating Scale (MADRS) is a ten-item diagnostic questionnaire which psychiatrists use to measure the severity of depressive episodes in patients with mood disorders.

Montgomery–Åsberg Depression Rating Scale (MADRS-s) - PRO

MADRS-s is a self-rating version of MADRS and correlates well with expert ratings. The MADRS-s instrument has nine questions, with an overall score ranging from 0 to 54 points. During the trial, each participant reports their MADRS-s score in the same way as normal customers would. The MADRS-s uses cut-off points detailed below to classify the severity of depressive symptoms:

- 0-12 points: None or very mild depression
- 13-19 points: Mild depression
- 20-34 points: Moderate depression
- ≥ 35 points: Severe depression

Hamilton Depression Rating Score (HDRS-17)

The HDRS (also known as the Ham-D) is the most widely used clinician-administered depression assessment scale. The original version contains 17 items pertaining to symptoms of depression experienced over the past week. The questionnaire is designed to be used by clinicians to rate the severity of depressive symptoms in adults by probing mood, feelings of guilt, suicide ideation, insomnia, agitation or retardation, anxiety, weight loss, and somatic symptoms.

Mini International Neuropsychiatric Interview (MINI) - ClinRO

The Mini-International Neuropsychiatric Interview (M.I.N.I.) is a short structured diagnostic interview, developed jointly by psychiatrists and clinicians in the United States and Europe, for DSM-IV and ICD-10 psychiatric disorders.

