22.2 SAMPLE SIZE ASSUMPTIONS AND CALCULATIONS

The sample size calculation is based on data from Brunoni et al (2017). The calculation is based on a two- sample t-test for mean difference with the following assumptions:

- Group difference in means = 3.2
- Standard deviation of Investigational and Sham groups = 7.1 and 7.9, respectively
- One-sided type I error = 0.025
- 80% power

The resulting sample size is 176 subjects. To obtain an increase in statistical power (87.6%), 216 subjects were chosen. Accounting for 20% attrition, the overall sample size will be 270 subjects.

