22.13 POOLABILITY ANALYSIS

Poolability will be assessed through stratification of the primary endpoint by Country (OUS and US). Within country point estimates will be calculated along with nominal descriptive 95% Confidence Intervals. The focus of this analysis will be on the similarity of the country specific point estimates. Differences will be described in the Clinical Study Report.

Statistical evaluation of the primary endpoint will be evaluated by adding site by treatment group term to the primary MMRM model. A p-value of ≤ 0.10 will be considered significant for this poolability assessment. Should a significant site x treatment group interaction be present, the patient factors of age, gender, and baseline scores will be assessed to understand if differences in case-mix factors explain differences observed between sites.

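### Protocol section 22.7 studies age as an effect modifier only through a median split, which costs about 25% to 36% of the information if the treatment effect changes roughly linearly with age; a cheap supportive model would recover it

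*Protocol*

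**What the plan says.** Section 22.7 states its purpose as follows: "The heterogeneity of treatment effects for the primary effectiveness endpoint will be examined for subgroups using baseline variables". On which variables, it says: "These will include, but are not limited to, age (split at median), and sex at birth". The model is the one used for the primary endpoint: "The mixed model for repeated measures will be run to see the impact of the treatment effect by each subgroup of interest separately". The output is equally definite: "The results will be reported as mean differences and 95% confidence intervals for each subgroup", to be drawn as a forest plot.

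Section 14 shows that the underlying variable is collected: "At screening, participant baseline characteristics including, but not limited to, age and gender, will be recorded". Section 12.2 admits anyone aged 18 or over, and the criteria set no upper limit, so the enrolled age range may be wide.

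The statistics section uses age in one other place, the poolability analysis of section 22.13. If the site-by-treatment interaction is significant, "the patient factors of age, gender, and baseline scores will be assessed to understand if differences in case-mix factors explain differences observed between sites". That check is conditional, concerns differences between sites and does not say in what form age enters.

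**The concern.** Section 22.7 does not leave the form of age open. It names the split and gives no second form; the wording that the list is not exhaustive opens the set of variables, not the way age is handled.

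Cutting at the median treats an 18-year-old and someone just under the median as the same, and two people just either side of it as different. If the device effect rises or falls gradually with age, the contrast between the halves is a less precise way to see it than a slope fitted to the recorded ages. Adding a treatment-by-age-group test would not restore this information, because it is lost when age is cut. The cut also falls wherever the sample median falls, so the two rows describe age groups that another study would not share.

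At stake is the precision of one exploratory estimate: how far the treatment difference depends on age.

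**Working it through.** **Inputs**
- From section 22.2: "Group difference in means = 3.2" and "Standard deviation of Investigational and Sham groups = 7.1 and 7.9, respectively"; one-sided type I error 0.025; 216 evaluable subjects; 270 after 20% attrition.
- From section 22.4: 1:1 allocation.
- Assumed: the shape of the age distribution (none is given), a linear change of effect with age, equal arms within each age half, and a simple Week 10 comparison in place of the mixed model.

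**The protocol's own figures reproduce.** The root mean square SD is √((7.1² + 7.9²)/2) = 7.51. A two-sample t calculation for a difference of 3.2 gives 88 per arm, or 176 in total, with 80.2% power. At 108 per arm, or 216 in total, power is 87.6%. Then 216/0.8 = 270. The protocol states no precision for the age analysis, so there is no figure of that kind to reproduce.

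**Information kept by the split.** For a linear treatment-by-age relation, the split's information relative to continuous age is the squared correlation between age and the above-median indicator. This equals (Δ / (2 × SD of age))², where Δ is the gap in mean age between the halves.
- Uniform ages over a range w: Δ = w/2 and SD = w/√12, so the ratio is (√12/4)² = 0.75, a loss of 25%.
- Normal ages: Δ = 2 × √(2/π) × SD, so the ratio is 2/π = 0.637, a loss of 36%.
- Normal ages truncated at 18 (assumed mean/SD 40/15 with an upper limit of 80, and 38/11) give losses of 33% and 34%. The right-skewed shapes tried gave 42% to 52%.

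For this question, 216 subjects count as 216 × 0.75 = 162 (uniform) or 216 × 0.637 = 138 (normal).

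**Precision in HDRS-17 points.** Each half has 108 subjects, 54 per arm.
- Variance of the treatment difference in one half: (7.1² + 7.9²)/54 = 112.82/54 = 2.089.
- SE of the difference between the two halves' effects: √(2 × 2.089) = 2.04.
- 95% CI half-width with the split: 1.96 × 2.044 = 4.0 points.
- The same contrast estimated from continuous age under linearity: 4.0 × √0.75 = 3.5 points (uniform), or 4.0 × √0.637 = 3.2 points (normal).

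**Power, for scale only** (two-sided 0.05). The standardised effect is D/2.044 for the split and D/(2.044 × √ratio) for continuous age, where D is the difference between the halves' effects.

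| D (points) | Split | Continuous, uniform ages | Continuous, normal ages |
|---|---|---|---|
| 3.2 | 1.57 → 35% | 1.81 → 44% | 1.96 → 50% |
| 1.6 | 0.78 → 12% | 0.90 → 15% | 0.98 → 17% |

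**How large the age effect must be for a conventional 80%.** Continuous age reaches 80% power at a standardised effect of 1.96 + 0.84 = 2.80. The halves would then differ by 2.80 × √0.637 × 2.044 = 4.6 points (normal) or 2.80 × √0.75 × 2.044 = 5.0 points (uniform). Both exceed the whole assumed treatment effect of 3.2.

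**The case against.** The case for leaving section 22.7 alone is reasonable. It plans a descriptive display, a forest plot needs categories, and a median split is a conventional way to make two equal halves. The rule is fixed in advance and depends only on enrolled ages, not on HDRS-17 results, so it is not open to an outcome-driven choice of cut. No test or alpha is attached to age. The recorded ages remain available, so nothing is lost for good. All of this stands, and it keeps the point minor.

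A reader might infer a larger cost: that a relation found with 80% power on continuous age is found with only 61% (normal) or 68% (uniform) after the split, a loss of 12 to 19 points. The arithmetic is right, but that starting point needs the halves' effects to differ by 4.6 to 5.0 points. The documents do not suggest age effects of that size, and section 22.7 plans no such test. At a difference of 1.6 points the gain is about 3 to 4 percentage points, and neither analysis is very informative.

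Two further reservations hold. The loss depends on an assumed age distribution and on a roughly linear relation. And the SAP is not at hand: it could contain a continuous-age model, so the statement that age is used only as a split is about this protocol.

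**Conclusion.** The point holds as a minor improvement. In this protocol the effect-modification analysis of age is confined to a median split although continuous age is recorded. Under a roughly linear relation that wastes about 25% to 36% of the information for uniform to normal ages, and more if ages are right-skewed. A true step at the median would lose nothing. In points, the 95% CI half-width for the contrast between age halves is about 4.0 with the split, against 3.2 to 3.5 if the same contrast is estimated from continuous age. Covariate adjustment in the mixed model could narrow all of these; the protocol gives no figure for that.

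It would be wrong to infer that the primary result is weakened. The primary test, its one-sided 0.025 level, the secondary hierarchy and the 270 subjects do not depend on this analysis.

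**What to change.** In section 22.7, and in the SAP if it does not already do so, add a supportive model for age. To the primary mixed model add continuous age, age by visit, treatment by age, and treatment by age by visit. Report the change in the Week 10 treatment difference per 10 years of age with its 95% CI, labelled exploratory. Keep the median-split rows in the forest plot for display.

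The cost is one sentence, one more model run and a few more parameters. The main downside is the assumed linear trend in age; the displayed split rows give a rough check on it. If the SAP already contains a continuous-age model, a reference to it in section 22.7 is enough.

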12.2 INCLUSION CRITERIA

To be eligible to participate in this study, participants must meet all the following criteria:

- 1. Be ≥18 years.
- Have a diagnosis of Unipolar MDD with a current depressive episode as defined by the diagnostic criteria in the Diagnostic and statistical manual of mental disorders – 5th edition (DSM-V
- 3. Have a Hamilton Depression Rating Score (HDRS-17) of \geq 16.
- 4. For 6 weeks prior to enrollment, are either:
 - a. not taking antidepressant medication or:

- b. are taking a stable antidepressant regimen with a stable medication source and agree to continue the same regimen throughout study participation
- 5. If in psychotherapy, have maintained stable psychotherapy for at least 6 weeks prior to enrollment.
- 6. Have access to a stable internet connection through which the treatment will be received.
- 7. Have access to a smartphone or other device running Android 5.0+ or iPhone Operating System (iOS) 12+ (e.g., reasonably new iPhone/iPad or Android phone), used to using the device in their everyday life, and can capably use the study application on the device, as determined by the investigator.
- 8. Are currently living in England/Wales (UK) or Texas (US).
- 9. Subject is currently under the care of a psychiatrist or a primary care physician, agrees to be evaluated at regular intervals by a psychiatrist or primary care physician for the duration of study participation, and agrees to promptly inform the study staff of any change of psychiatric or mental health providers during study participation.
- 10. Subject agrees to allow any and all forms of communication between the investigators/study staff and any healthcare provider who currently provides and/or has provided service to the patient/subject within at least two years of study enrollment.
- 11. Subject agrees to provide the name and verifiable contact information (email and mailing addresses, mobile and land-line phone numbers, as applicable) of at least two persons ≥ age 18 who reside within a 60-minute drive of the patient's residence and whom the research staff is at liberty to contact, as they deem necessary, for the duration of study participation.
- 12. Be able to give voluntary, written informed consent to participate and have signed an Informed Consent Form specific to this study.
- 13. Be willing and able to comply with all study procedures.

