- 14. Subject agrees to meet all of the inclusion criteria throughout their participation in the study. Otherwise, the subject will be discontinued from the study.
- 15. Subject agrees to a Safety/Suicide Risk Management Protocol, which is intended to reduce the reduce the risk of suicide during study participation.

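### Section 22.7 promises subgroups from baseline variables, then defines the antidepressant subgroup by use during the trial, so its treatment contrast is not a randomised comparison

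*Protocol*

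**What the plan says.** Protocol section 22.7 sets a general rule: "The heterogeneity of treatment effects for the primary effectiveness endpoint will be examined for subgroups using baseline variables". Age split at the median and sex at birth are its examples. It then adds a further group: "Subjects on antidepressants and/or psychotherapy drugs during the course of the trial will constitute their own subgroup", to be characterised and described in the clinical study report. The sentence after that applies the model to every subgroup: "The mixed model for repeated measures will be run to see the impact of the treatment effect by each subgroup of interest separately". Mean differences with 95% confidence intervals are to be reported for each subgroup and drawn in a forest plot.

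Eligibility (section 12.2) bears on how much medication can change. Criterion 4 admits subjects who, for 6 weeks before enrollment, take no antidepressant or "are taking a stable antidepressant regimen with a stable medication source and agree to continue the same regimen throughout study participation". Criterion 5 reads: "If in psychotherapy, have maintained stable psychotherapy for at least 6 weeks prior to enrollment". Criterion 14 adds: "Subject agrees to meet all of the inclusion criteria throughout their participation in the study. Otherwise, the subject will be discontinued from the study". Exclusion 35 (section 12.3) likewise discontinues anyone who meets an exclusion criterion during participation.

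**The concern.** Age and sex are fixed before randomisation, so active and sham subjects within each level remain randomised groups. Medication use during the trial is not fixed. A subject who is not improving may start an antidepressant, and non-improvement is expected to be more common on sham if the device works. Such a subject enters the on-medication subgroup because of an outcome that the arm influences. The active and sham members of that subgroup then differ in ways randomisation did not balance.

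At stake is how the forest plot is read. A difference between the medicated estimate and the overall effect could come from the way the subgroup was formed and be taken for effect modification by medication.

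**Working it through.** **1. The texts side by side.** The rule is subgroups "will be examined for subgroups using baseline variables". The definition refers to the course of the trial. Both stand in section 22.7, and only the first is a pre-randomisation classification. The sentences on the model, the intervals and the forest plot do not exempt the medication subgroup.

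**2. Do other rules make the two definitions equal?** Not fully.
- Only the second limb of criterion 4 carries an agreement to continue; the first limb looks back over 6 weeks. Criterion 5 also looks back only.
- Criterion 14 and exclusion 35 remove subjects from the study, but section 15.6 keeps their collected data in the analysis.
- The mITT set (section 22.3.3), used for the primary endpoint, excludes untreated subjects and those randomised in error, not those who start a drug. Only the per-protocol set (section 22.3.4) excludes new treatments, and only those listed as exclusion criteria.

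**3. The protocol's planning figures.** Section 22.2 gives a difference of 3.2, SDs of 7.1 and 7.9, and one-sided alpha of 0.025. The average SD is √((7.1² + 7.9²)/2) = 7.51. The noncentral t gives 88 per arm, 176 in total (power 80.2%), and 87.6% power at 108 per arm. 216/0.8 = 270. All agree with the protocol, and none depends on the subgroup definition.

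**4. Simple illustration.** Every rate here is an assumption: 135 per arm; 60% on medication at baseline (81 on, 54 off); 10% of off-medication sham and 4% of off-medication active subjects start; starters are 5 points worse than the rest of the group they leave or join.
- On medication, sham: 54 × 0.10 = 5.4 starters; 5.4/86.4 × 5 = 0.31 worse.
- On medication, active: 54 × 0.04 = 2.16 starters; 2.16/83.16 × 5 = 0.13 worse.
- Net: 0.31 − 0.13 = 0.18 points added to the on-medication effect.
- Remainder: sham gains 0.10 × 5 = 0.5 and active 0.04 × 5 = 0.2, so the effect falls by 0.3.

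**5. Against sampling error.** With the planning SDs, the standard error at 81 per arm is √((7.1² + 7.9²)/81) = 1.18, a 95% half-width of 1.96 × 1.18 = 2.3. At 54 per arm it is 1.45, a half-width of 2.8. The shifts are about 0.15 and 0.2 standard errors.

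**6. Harsher illustration.** A simulation of 2,000,000 subjects per scenario set a true effect of 3.2 in everyone and an assumed mean sham improvement of 8 points. Off-medication subjects whose improvement fell below a cutoff started a drug, with no effect on outcome and no discontinuation. Baseline-defined subgroups returned 3.18 to 3.23. Subgroups defined by use during the trial gave:

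| On at baseline | Sham start rate | On | Off | Difference |
|---|---|---|---|---|
| 40% | 2% | 3.66 | 2.87 | 0.79 |
| 40% | 5% | 4.01 | 2.54 | 1.47 |
| 40% | 10% | 4.34 | 2.15 | 2.19 |
| 40% | 20% | 4.31 | 1.61 | 2.70 |
| 60% | 2% | 3.40 | 2.90 | 0.50 |
| 60% | 5% | 3.59 | 2.56 | 1.03 |
| 60% | 10% | 3.76 | 2.15 | 1.61 |
| 60% | 20% | 3.82 | 1.63 | 2.19 |

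With no starts, the two definitions coincide.

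**The case against.** The best defence is that the design already fixes medication status. Subjects enter with no antidepressant or a stable regimen, and those who cease to qualify leave the study. For a compliant subject, use during the trial equals use at baseline, and the sentence is loose wording for that. This largely stands as a limit on size: what remains is deviators. It does not cure the definition, because deviators' data stay in the mITT analysis and deviation can depend on arm.

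A second defence is that the group is only to be characterised and described. That reading is possible but weaker, since the model and forest plot follow for each subgroup without exception.

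Some stronger readings are tempting but not supported:
- That regimen changers merely stop treatment and are followed as usual. The criteria say discontinued from the study; section 15.4 disables the device of withdrawn subjects and offers only an optional termination visit. Neither illustration models this.
- That two complementary subgroups are biased in opposite directions. The protocol names no off-medication subgroup.
- That the direction is known. Both illustrations give the started drug no benefit; an effective drug could shrink or reverse the shift.
- That the result is central to labelling. Neither the primary objective (section 10.2) nor the multiplicity plan (section 22.10) mentions medication status.
- That drugs started in the open-label phase would count. The wording does not exclude them, but the section concerns the week-10 endpoint.

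**Conclusion.** The contradiction within section 22.7 is plain and does not depend on any assumption. As written, the medication subgroup conditions on a status that response, and hence arm, can affect, so its contrast is not a randomised comparison. This is a definition the protocol itself states, not a detail left to the SAP.

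The practical size is unknown. It is about 0.2 to 0.3 points under the simple assumed rates, well inside the subgroup's sampling error. In the harsher simulation the spurious on/off difference is about 0.5 to 2.7 points. It is zero if nobody changes medication. Those figures show a possible range, not an estimate. The primary test, its error rate and the sample size are untouched, and no formal test is attached to the subgroup. The wording should be corrected, but the trial's main conclusion does not rest on it.

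**What to change.** Reword the sentence in section 22.7 so that the subgroup is defined by antidepressant or other MDD medication status recorded at screening or at week 0 before randomisation. Table 1 already schedules concomitant medication review at both points, and section 18 covers medication given for MDD, so this part costs one sentence and no new data.

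State what psychotherapy drugs means. If psychotherapy itself is intended, use baseline status as ascertained for inclusion criterion 5, provided it is recorded: the protocol shows an eligibility condition, not a yes/no data field, so a field may have to be confirmed or added.

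Report medication started or changed after randomisation in the blinded phase descriptively by arm. Table 1 schedules medication review at weeks 1, 4, 7 and 10, so the source data are already planned. The sample size and primary analysis do not change.

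### Section 22.7 sets out to examine heterogeneity of the treatment effect but, as written, fits the model by subgroup and does not directly estimate or report the between-subgroup difference

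*Protocol*

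**What the plan says.** Protocol section 22.7 states the aim: "The heterogeneity of treatment effects for the primary effectiveness endpoint will be examined for subgroups using baseline variables". On the factors it says: "These will include, but are not limited to, age (split at median), and sex at birth". Subjects on antidepressants and/or psychotherapy form a further subgroup. The method follows: "The mixed model for repeated measures will be run to see the impact of the treatment effect by each subgroup of interest separately". The output is then fixed: "The results will be reported as mean differences and 95% confidence intervals for each subgroup", displayed in a forest plot.

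The section names no treatment-by-subgroup term, interaction estimate or interaction p-value. It does not refer to the SAP, whereas sections 22.5.1, 22.6 and 22.10 do so for the MMRM details, missing data and multiplicity.

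Section 22.13 treats site differently. It gives country-specific estimates with descriptive intervals, and it also assesses site by "adding site by treatment group term to the primary MMRM model", with p ≤ 0.10 as the threshold.

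**The concern.** The aim and the method do not quite meet. Whether an effect is heterogeneous is a question about the difference between two subgroup effects. Separate fits answer another question: how large the effect is within each subgroup, and how precisely it is known there.

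Subgroup intervals are much wider than the overall one, so some will include zero even when the effect is the same everywhere. With only those intervals in view, it is easy to read one row that excludes zero and another that does not as evidence that the device works in one group and not in the other. The list of factors is open, which gives more chances for such a pattern. Section 24.4 says the data are to support a premarket approval application, so a mistaken subgroup impression could carry weight.

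**Working it through.** **Inputs (protocol sections 22.2 and 22.4).** "Group difference in means = 3.2"; SDs 7.1 (active) and 7.9 (sham); one-sided alpha 0.025; 1:1 allocation; 216 evaluable subjects; 270 randomised after 20% attrition.

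**Reproducing the plan's own figures.** Common SD = sqrt((7.1² + 7.9²)/2) = sqrt(56.41) = 7.51. The t-test needs 88 per arm, or 176 in total, for 80% power. Power at 108 per arm is 87.6%, and 216/0.8 = 270. All three stated figures reproduce.

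**Precision within one half of a median split, N = 216 (54 per arm per half).**
- SE = sqrt((7.1² + 7.9²)/54) = sqrt(112.82/54) = 1.45 points.
- Half-width of the 95% interval = 1.96 × 1.445 = 2.83 points.
- Power for a true 3.2 = Φ(3.2/1.445 − 1.96) = 0.60 by normal approximation, or 0.592 by the t-test.

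**Chance of a discordant pair when the true effect is 3.2 in both halves.** The halves are disjoint, so P(exactly one interval excludes zero) = 2p(1 − p).
- N = 216: 2 × 0.592 × 0.408 = 0.48. Simulation with 200,000 replicates gives 0.481.
- N = 270 (67.5 per arm per half, SE 1.29, p = 0.697): 2 × 0.697 × 0.303 = 0.42.

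With an uneven split, p₁(1 − p₂) + p₂(1 − p₁) gives:

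| Split (50:50 is the planned age split; others illustrative) | N = 216 | N = 270 |
|---|---|---|
| 50:50 | 48% | 42% |
| 70:30 | 55% | 51% |
| 80:20 | 63% | 62% |

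At N = 216, with two balanced factors (assumed for age and sex), at least one discordant pair appears in about 64% of simulated trials.

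**The direct contrast, N = 216, 50:50.**
- SE of the difference between halves = 1.445 × sqrt(2) = 2.04 points, twice the overall SE of sqrt(112.82/108) = 1.02.
- With no true heterogeneity, a two-sided 5% interaction test rejects in 5% of trials (simulated 5.0%). Among discordant pairs it rejects in about 10%.
- Power for a subgroup difference of 3.2, as large as the whole assumed effect: Φ(3.2/2.04 − 1.96) ≈ 35%.
- Difference detectable with 80% power: (1.96 + 0.84) × 2.04 ≈ 5.7 points.

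**The case against.** The strongest reply is that section 22.7 promises a description, not a test. It says heterogeneity will be examined, sets no decision rule and promises no subgroup p-values. A forest plot of estimates and intervals is a conventional display. This stands. The 42% to 48% therefore measures what happens to a reader who contrasts rows by whether each interval excludes zero. The protocol does not prescribe that reading, and comparing the estimates with their intervals is less misleading.

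The wording can also be read as one factor at a time rather than one model per level, which would be compatible with an interaction model. That reading is possible but less natural, and the stated output still omits the contrast.

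The SAP is not shown and could add an interaction term. The point therefore holds for the protocol text only. It is not simply detail left for later, because section 22.7 itself fixes the method, output and display.

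Section 22.13 also starts from country-specific estimates and puts its focus on their similarity, and its interaction serves poolability. That is so, but it reports the interaction as well as the estimates, and 22.7 does not.

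Two stronger readings are tempting and should be resisted:
- **That nothing in the planned output allows the subgroups to be compared.** The age halves and the sexes are disjoint, so the difference and its SE, sqrt(SE₁² + SE₂²), follow from the two reported intervals. What is missing is the direct estimate, not the information.
- **That separate fits lose precision.** No loss is shown. The 2.04 above is itself the SE from separate halves.

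**Conclusion.** The point holds as a minor one about reporting and interpretation. Section 22.7 states a heterogeneity aim, yet the method and output it fixes stop at within-subgroup effects.

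With identical effects of 3.2 in both halves of a median split, a discordant pair would appear in about 42% (N = 270) to 48% (N = 216) of trials for a reader who compares significance, against 5% false positives for an interaction test. The SE of the between-half difference is about 2.0 points at N = 216, and a forest plot of subgroup rows does not print it.

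These figures assume the effect and SDs of section 22.2 and no precision gain from the MMRM. The 270 figure also assumes full information from every randomised subject, so it is the favourable end.

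A reader might infer that the trial's conclusions are at risk. The documents do not support that: the primary test, alpha, sample size and secondary testing order do not depend on section 22.7.

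**What to change.** Amend section 22.7 so that, for each baseline subgroup factor, one MMRM is fitted to all subjects with treatment × visit × subgroup terms and the lower-order terms. Report the Week 10 treatment-by-subgroup estimate with its 95% interval beside the subgroup estimates in the forest plot.

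Label it exploratory and state its low power (about 35% for a 3.2-point difference at N = 216), so that a wide interval around zero is not taken as proof of a uniform effect. An estimate with its interval serves better here than a pass/fail test. If the SAP already contains such a contrast, align the protocol sentence with it.

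The cost is a sentence or two of text and a few model terms per factor. Data collection, sample size and trial conduct do not change, and the approach matches the interaction already planned for site in section 22.13.
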